#### Sensitivity Analyses

A per protocol analysis will be performed for the key secondary analysis of change in total SGRQ score.

If the graphical presentations over time indicate a linear trend a similar slope model as for the similar slope model as for the primary endpoint of rate of decline in FVC may be performed as a supportive analysis for SGRQ.

# 9.3.6. Other Questionnaires

The following questionnaires will be completed electronically, using a tablet device at the clinical study center.

#### 9.3.6.1. EQ-5D

#### EQ-5D will not be analysed for the abbreviated CSR.

The 3-level version of EuroQOL 5-Dimensions Questionnaire (EQ-5D-3L) consists of two pages:

*– EQ-5D descriptive system:* 

The EQ-5D descriptive system is split into five domains: mobility, self-care, usual activities, pain/discomfort, and anxiety/depression. Each dimension has three levels, which results in a 1-digit number that expresses the level selected for that dimension. The digits for the five dimensions can be combined into a 5-digit number that describes the subject's health state (e.g. '11231'). Results will be presented as frequency of subjects having no problem, some

problems, and high problems in each domain. In addition, the 5-digit number will be converted into a single summary index score applying a formula that applies weights to each of the levels in each domain. The formula (value set) is obtained from EuroQol Research Foundation and is derived according to the preferences of the general population of a country / region (EuroQol Research Foundation. EQ-5D-3L User Guide, 2018).

EuroQOL visual analogue scale (EQ VAS)
 The EQ VAS records the subject's self-rated health on a vertical VAS and can be used as a quantitative measure of health outcome that reflects the subject's own judgment.

*EQ-5D* and *EQ VAS* will be presented using descriptive statistics by treatment group of actual values and changes from baseline at all time points.

# 9.3.6.2. Leicester Cough Questionnaire (LCQ)

LCQ will not be analysed for the abbreviated CSR.

Subjects with IPF commonly present with a (severe) non-productive cough. Cough will be evaluated using the LCQ. The LCQ is a 19-item questionnaire (Appendix 4) split into three domains: physical, psychological, and social. Scores are calculated by domain (range from 1 to 7) by summing the items and dividing by the number of completed items. Then these scores are added to obtain the total score (range from 3 to 21, with higher scores indicating a better health status).

Domains (questions):

- *Physical: 1,2,3,9,10,11,14,15*
- Psychological: 4,5,6,12,13,16,17
- Social: 7,8,18,19

*Domain scores: total score from items in domain/number of items completed in domain (range 1-7).* 

*Total scores: addition of domain scores (range 3–21).* 

LCQ total score and domain scores will be presented using descriptive statistics by treatment group of actual values and changes from baseline at all time points.

# 9.3.6.3. King's Brief ILD Questionnaire (K-BILD)

K-BILD questionnaire will not be analysed for the abbreviated CSR.

The K-BILD health status questionnaire is a 15-item questionnaire split into three domains: psychological, breathlessness and activities, and chest symptoms. Scores are weighted, using information obtained from the authors (Patel, et al., 2012) such that every domain score and the total score range from 0 to 100, with higher scores indicating a better health status. If an item is not completed it will not be counted in the numerator.

The final K-BILD questionnaire consisted of 15 items and three domains:

- breathlessness and activities (questions 1, 4, 11, 13)
- psychological (questions 3, 5, 6, 8, 10, 12, 14)
- chest symptoms (questions 2, 7, 9)

*K-BILD* total score and domain scores will be presented using descriptive statistics by treatment group of actual values and changes from baseline at all time points.

### 9.3.6.4. VAS Cough and Urge to Cough

VAS Cough and Urge to Cough will not be analysed for the abbreviated CSR.

VAS Cough and Urge to Cough will use a VAS of 100 mm with extremes "no cough" to "worst possible cough", and "no urge" to "highest urge to cough". VAS Cough and Urge to Cough will be presented using descriptive statistics by treatment group of actual values and changes from baseline at all time points.

# 9.3.7. Functional Exercise Capacity and

For the abbreviated CSR only the 6MWT distance and

will be analysed.

The actual values and changes from baseline in 6MWT total distance walked in 6 minutes, will be presented descriptively for each time point by treatment group.

Given is measured in a resting state during the scheduled visits and during exercise in the context of the 6-MWT, these will be presented separately. In addition to the descriptive statistics,

will be presented during the study as well as per visit (see Appendix 8 of the protocol for the definition of the normal range).

#### 9.3.8. DLCO

Change from baseline in DLCO (corrected for Hb, expressed in mmol/min/kPa) and percent predicted from normal (%) will be summarized per time point and treatment group by descriptive statistics.

#### 9.3.10. Subgroup Analyses

Descriptive statistics will be provided within subgroup for the primary endpoint of rate of decline in FVC at Week 52. A similar random coefficient regression model with an additional term for the treatment-by-subgroup interaction will be used to estimate the LS means per treatment group and LS mean differences (with 95% CIs) for each subgroup. Results will be graphically presented for the LS mean difference using a forest plot. The following subgroups will be evaluated:

- Age (<65 and  $\geq$ 65 years)
- Sex
- Race
- Stratum
- Geographic region (NA, EMEA, Latin-America, Asia-Pacific)

Given the two studies are identically designed, more subgroups may be investigated based on the pooled data to increase the size of certain small subgroups.

Summaries may also be provided for the efficacy and	d	endpoints by	
subgroups.		•	

9.3.11.				

# 9.4. Safety Analyses

Safety analyses will be performed using the FAS.

Continuous variables will be summarized using descriptive statistics. Frequencies and percentages will be generated for categorical variables. No formal testing will be performed to compare the treatment groups.

Safety tables will be presented by treatment group, as randomized.

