# 3.3. Full Analysis Set (FAS)

All randomized subjects who received at least one dose of IP.

All data will be included irrespective of IP interruption or termination and changes in standard of care. Only efficacy data after lung transplant will be excluded.

If a subject is unblinded (e.g. in case of a serious adverse event [SAE]), all data of this subject recorded in the database will be included in the analyses.

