# 5. TREATMENT GROUPS

# 5.1. Randomized Versus Actual Treatment

For efficacy, and safety analyses, the treatment group as assigned by the randomization will be used in the analysis (i.e. as-randomized analysis).

For PK analyses, the actual treatment will be used in the analyses.

Differences between as-treated and as-randomized will be flagged in the listing of subject randomization.

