# 9.2.6. Exposure to IP and Compliance

The following parameters will be calculated for the compliance and extent of exposure to IP:

- Overall compliance (%) = 100 x (number of tablets actually used) / (number of tablets that should have been used, according to the randomization).
- Total treatment duration (days) = last dose of IP intake date first dose of IP intake date + 1 day.
- Total treatment duration, excluding days off drug (days): sum of all durations (last first +1) in the drug log pages where there is at least one dose taken, i.e. the sum of the number of days with at least one dose of IP.

- Percentage days with an intake =  $100\% \text{ x} \left(\frac{\text{total treatment duration, excluding days off drug}}{\text{total treatment duration}}\right)$
- Total compliant treatment duration (days): sum of all durations (last first +1) in the drug log pages where there is a dose with exactly 3 tablets.
- Percentage compliance of treatment duration =  $100\% \times \left(\frac{\text{total compliant treatment duration}}{\text{total treatment duration}}\right)$

Similar calculations will be done using only the data up to Week 52.

Summary tables will be provided for the different compliance and extent of exposure parameters by treatment and overall. In addition, frequency tables will also be provided for the compliance parameters (overall compliance, percentages days with an intake and percentage compliance of treatment duration), using the following categories: <80%,  $\ge80\%$ -<100%, 100%, >100%- $\le120\%$ , >120%.

Frequency tables with the number of subjects who had at least one down-titration and with the number of subjects who had at least one dose interruption, and the reasons for down-titration and interruption by treatment group and overall, will also be provided.

Patient-years of exposure to IP by treatment group and overall.

The same tables will be created by stratum and treatment.

A listing will be provided of the subjects who took incorrect IP for at least part of the treatment period, all prime therapy records are to be included to provide an overview of the amount of incorrect treatment relative to the total treatment period.

In addition, listings of the subjects who had their IP down-titrated and interrupted for at least part of the treatment period will be provided, all prime therapy records are to be included to provide an overview of the amount of down-titration and interruption relative to the total treatment period.

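### Safety tables are grouped by randomised arm only, so if any subject took IP from another arm, the resulting events are counted in the randomised arm and safety differences tend to shrink

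*SAP*

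**What the plan says.** The grouping rule is deliberate and appears twice. SAP 5.1 reads: "For efficacy, and safety analyses, the treatment group as assigned by the randomization will be used in the analysis (i.e. as-randomized analysis". The next sentence there treats PK differently: "For PK analyses, the actual treatment will be used in the analyses". SAP 9.4 repeats the rule for safety output: "Safety tables will be presented by treatment group, as randomized".

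The safety population does not depend on which drug was taken. SAP 9.4 says: "Safety analyses will be performed using the FAS". SAP 3.3 defines that set as: "All randomized subjects who received at least one dose of IP". Protocol 7.3.5 also runs safety on the FAS by treatment group, without saying whether the group is the assigned or the received one. Neither document defines an as-treated safety set.

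The SAP deals with wrong-drug exposure through two listings. SAP 5.1: "Differences between as-treated and as-randomized will be flagged in the listing of subject randomization". SAP 9.2.6: "A listing will be provided of the subjects who took incorrect IP for at least part of the treatment period"; that listing includes the full therapy records, so the extent of the error can be seen. No adverse event, laboratory, ECG or vital-sign table by treatment received is planned, not even as a sensitivity table.

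**The concern.** Analysing by assigned arm suits efficacy: it preserves the randomised comparison, and any mixing of treatments generally works against finding a benefit. For safety the same mixing works the other way. An event on active drug in a placebo-assigned subject raises the placebo rate, and a placebo-treated subject in an active arm lowers the active rate. Both tend to make the drug look closer to placebo.

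Safety testing is descriptive, but comparative estimates are reported. SAP 9.4.1.6.1 and 9.4.1.6.2 tabulate differences from placebo with 95% CIs (Miettinen and Nurminen), and SAP 9.4.2.9 reports liver elevations by level and in combination with bilirubin. SAP 1 keeps safety among the analyses for the abbreviated CSR. A listing lets a reader find an affected subject, but it changes no rate, difference or interval.

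Errors are possible because supply is repeated. Treatment numbers are assigned at each visit (protocol 4.6.1), several kits are dispensed per visit, and direct-to-patient shipment was added for COVID-19 (protocol 5.3).

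**Working it through.** The plan states no figure on this point, so there is none to reproduce. The check covers the rule itself and the possible size of its effect.

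**Inputs.** 250 subjects per arm (protocol 4.6.1). The number on incorrect IP is not given, so m = 1 to 25 per arm is assumed for illustration. Event risks of 10% vs 5% and 4% vs 1% are also assumed.

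**Full-period symmetric swap.** Let a share f = m/250 of the active arm take placebo throughout, and the same share of the placebo arm take active. With true risks pA and pP:

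- observed active risk = (1 - f)pA + f·pP
- observed placebo risk = (1 - f)pP + f·pA
- observed difference = (pA - pP)(1 - 2f)

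| m per arm | f | 1 - 2f | true 5.0 points (10% vs 5%) appears as | true 3.0 points (4% vs 1%) appears as |
|---|---|---|---|---|
| 1 | 0.4% | 0.992 | 4.96 | 2.98 |
| 2 | 0.8% | 0.984 | 4.92 | 2.95 |
| 5 | 2.0% | 0.960 | 4.80 | 2.88 |
| 12 | 4.8% | 0.904 | 4.52 | 2.71 |
| 25 | 10% | 0.800 | 4.00 | 2.40 |

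If the error runs one way only (say, placebo-assigned subjects taking active), the factor is (1 - f), half the loss. Swaps between 200 mg and 600 mg move the two active arms toward each other and do not follow this formula against placebo.

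**Part-period error.** Supply runs to the next scheduled visit (protocol 5.3). By the visit schedule in protocol 4.1, the longest interval up to Week 52 is 10 weeks (Week 42 to 52), and it is 12 weeks after that. For a subject who stays on treatment to the next visit, one wrong dispensing is therefore at most about 10/52 = 19% of exposure, or 12/64 = 19% in the first interval after Week 52. If events accrue in proportion to time on each drug (an assumption), a share g of exposure on the wrong drug gives a factor of about (1 - 2fg). With m = 5 and g = 0.19: 1 - 2 × 0.02 × 0.19 = 0.992, against 0.960 for the full period. The share g is larger for a subject who stopped early, including through the study halt, or whose interval was stretched under the COVID-19 windows in protocol 6.1.1.

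**Rare events.** Moving one subject's event from the placebo column to an active column changes the difference by about 1/250 + 1/250 = 0.8 points. This is small for common events but visible for a finding with only a few cases, such as combined transaminase and bilirubin elevation.

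**The case against.** The strongest reply is that no problem has been shown. A planned listing covers a contingency and is not evidence of errors. The IWRS gives the treatment number for each subject at each visit (protocol 4.6.1). SAP 9.2.6 does not define incorrect IP, and each kit holds blisters for three dose levels (protocol 4.1.2), so the listing could include errors within the correct arm. The rule is disclosed twice, affected subjects can be identified from the listings, and there is no formal safety testing. All of this stands, and it limits the weight of the point. It does not supply a rate or interval by treatment received.

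A second reply is that a simple as-treated rule may not help. If each subject is assigned to the drug taken for most of the exposure, a single wrong dispensing of about 19% leaves the subject in the randomised arm. A reassigned subject would carry events on the correct drug into the other arm. That is right, and it is why a rule for part-period errors is needed.

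A reader might infer that this grouping distorted the benefit-risk conclusion that ended the studies. The documents do not support that. SAP 1 attributes the conclusion to the IDMC's own review of unblinded data, before this SAP version, and neither document says how the IDMC grouped subjects. A reader might also infer that events were in fact credited to the wrong arm; neither document says that any subject took another arm's IP. Protocol-permitted down-titration is not incorrect IP and is no part of this point.

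**Conclusion.** The point holds as a conditional, minor one. The SAP foresees incorrect IP, groups every safety table by assignment and answers mismatches with listings alone. If any subject took IP from another arm, the CSR safety tables and their intervals will tend to understate active-versus-placebo differences.

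The effect is negligible for common events if one or two subjects per arm are affected (at most 1.6% of the difference for a full-period symmetric swap of two). It reaches 10% to 20% only if 12 to 25 of 250 per arm were swapped throughout, and nothing in the documents suggests that. The (1 - 2f) factor assumes symmetric, full-period swaps between one active arm and placebo; one-way and part-period errors dilute less. What is at stake is the accuracy of the CSR safety record.

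**What to change.** Amend SAP 5.1 and 9.4 so that safety tables are grouped by treatment actually received, leaving efficacy as randomised. Because part of the study team is already unblinded (SAP 2.7), a cleaner alternative is to keep the as-randomised tables and, if any subject took incorrect IP, add as-treated tables for TEAEs, serious TEAEs, deaths and liver elevations.

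In either case:

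- Define incorrect IP so that drug from another arm is separated from a wrong dose level within the assigned arm.
- State a rule for part-period errors. For example, attribute each event to the IP being taken at onset (the last IP taken, if onset falls in the 30 days after the last dose), with person-time split to match.
- Footnote the affected subjects in each table.
- If nobody took another arm's IP, say so in one CSR sentence; that closes the point.

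The cost is low. SAP 5.1 already requires as-treated differences to be identified, and SAP 9.2.6 already assembles the therapy records. What is added is the event-level attribution, a few tables, and a change after unblinding that SAP 9.1 allows if it is explained in the CSR.

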# 9.4.1. Adverse Events

AEs will be coded according to the most recent version of the Medical Dictionary for Regulatory Activities.

A listing will be provided for all available coding steps between AE verbatim and AE system organ class, mentioning also the subjects who had the AE.

# 9.4.1.1. Treatment-Emergent Principle.

All adverse events starting on or after the first dose of IP and up to the last dose plus 30 days, are considered treatment-emergent adverse events (TEAE).

All AEs and changes in attributes (worsening and improvement) of AEs are reported in the database. Only worsenings of a pre-existing adverse event, after first dose of IP up to the last dose plus 30 days are to be considered as a TEAE, improvements after first dose of IP are not. A worsening is defined if at least one of the attributes of the events worsens (severity, seriousness, relationship or action taken).

Selected tables will also be created for all AEs (or worsenings) which started after the first dose of IP (till the end of the study). Adverse events starting before the first dose of IP and improvements will be excluded, but will be in the listings.

# 9.4.1.2. Allocation of Adverse Events to Analysis Periods

All adverse events records will be placed into analysis periods considering their start date and flag indicating the relative timing versus study (drug) start, aiming to report the incidence of these events only in the analysis period during which they started.

The general rule for allocation of AEs to analysis periods follows:

Analysis period start date  $\leq$  AE start date  $\leq$  analysis period end date

If the start date of an AE is missing or incomplete to a level preventing a clear allocation of the AE to one single analysis period, a worst-case consideration (see below) will be done aiming to allocate the AE record to one single analysis period, if possible. When a worst-case consideration is needed, the end date of the AE record, if and as available, and the flag indicating the relative

timing versus study end should also be considered; if such AEs clearly ends on a given point, this will exclude the possibility to allocate the AE to an analysis period after that point.

- An AE which according to the available information of its start date could belong to the screening as well as to the analysis period with treatment will only be placed in the analysis period with treatment.
- An AE which according to the available information of its start date could belong to an analysis period with treatment as well as to a next analysis period for which no treatment is defined (follow-up) will only be placed in the analysis period with treatment.
- An AE with a missing start date will be allocated to the analysis period with treatment.

# 9.4.1.3. Treatment Relatedness

Following (ICH-E3), the drug relatedness will be dichotomized as follows:

Drug related: at least possibly drug related as assessed by the investigator, OR with missing drug relatedness (= worst-case)

Not drug related: less than possibly drug related.

In tabulations this dichotomized parameter will be used, but in the listings the original parameter will be presented.

# 9.4.1.4. Worst-Case Principle

When cross-tabulating AE preferred terms versus an AE attribute (e.g. severity), the worst-case is always applied within each analysis period, i.e. when a subject has multiple times the same AE preferred term starting in the same analysis period, then the subject is reported only once: only with the worst severity. If this happens in two different analysis periods, the AE is reported twice: once in each analysis period.

# 9.4.1.5. Adverse Event Onset Day and Durations

For each newly reported event, and reported worsening or improvement of an existing event, the start day in the study (the day of the AE start date relative to the date of first IP administration), the start day in the analysis period, and the duration (in days) will be calculated. In addition, the relative days and duration will be derived for the entire event; that is, the full evolution of the event, including the initial reporting and all subsequent worsenings and/or improvements. Relative start- and end days of the entire event will be derived based on the start date of the first event and the end date of the last event respectively; and the duration of the entire event will be calculated by subtracting the start date of the first event of the end date of the last event + 1 day.

See section 6.1 for the calculation of relative days.

# 9.4.1.6. Analyses

### 9.4.1.6.1. Treatment-emergent AEs during the treatment period

A summary table of the number of subjects with at least one TEAE, at least one IP/SOC related TEAE, one serious TEAE, a TEAE leading to death, TEAEs by worst severity, and TEAE leading to IP/ SOC discontinuation, down-titration and interruption per treatment group will be provided. The table will also include the difference in percentage of subjects with an TEAE from placebo for each of the two dose groups, together with the 95% CI using the method of Miettinen and Nurminen (Miettinen & Nurminen, 1985).

The number (percent) of subjects with a TEAE by system organ class and preferred term will be presented. Similar tables will be provided by worst severity, by IP/SOC relationship and, by worst severity and relationship. Furthermore serious TEAEs, deaths, TEAEs leading to IP/SOC down-titration, TEAEs leading to IP/SOC interruption and TEAEs leading to IP/SOC discontinuation will be tabulated by system organ class and preferred term.

A table will also be presented, with the difference from placebo and 95% CI based on the method of Miettinen and Nurminen for the number (percent) of subjects with a TEAE by system organ class and preferred term, for events with an incidence of at least 5% in at least one of the treatment groups (600, 200 mg or placebo).

Kaplan-Meier estimates will be presented graphically and in tabular format for the following time to first event endpoints, by treatment, as well as by treatment and stratum:

- first TEAE
- first serious TEAE
- first TEAE leading to early IP discontinuation

Treatment-emergent COVID-19 infections and suspected infections will be tabulated and listed.

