4.6. Measures to Minimize Bias

4.6.1. Randomization

At screening, subjects will be assigned a subject identification number. When a subject is confirmed to be eligible for the clinical study, he/she will be randomized.

A total of approximately 750 subjects will be randomized in a 1:1:1 ratio to receive GLPG1690 600 mg q.d., GLPG1690 200 mg q.d., or matching placebo for at least 52 weeks. Allocation of each subject to a given treatment will be described in a randomization list prepared by a CRO. This randomization list will be stratified in a balanced manner for background local standard of care for treatment of IPF (nintedanib, pirfenidone, or neither). Recruitment may stop earlier in one or more strata to maintain the balance as indicated, while the other strata(s) continue to recruit. Upon qualification for the study, allocation of each subject to a given treatment will be done using a centralized electronic system (interactive web response system [IWRS]) with permuted blocks.

For each subject at each visit, the clinical study center will contact the IWRS for the appropriate treatment number to be assigned. Each medication kit will contain the relevant IMP for the period until the next visit.

Subjects and study personnel will be blinded to the treatment assignment. Additional details on blinding and unblinding are provided in Section 4.6.2.

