- the first scheduled visit after their Early Treatment Discontinuation (ETD)
- The Week 26 visit (if not done before IP discontinuation)
- the Week 52 visit (if not done before IP discontinuation)
- after Week 52, visits every 24 weeks up to End of Study Assessments (EoSA), as described in Section 6.11.2 of the CSP.

For procedures in case of ETD, refer to Section 4.5.4 of the CSP. In the exceptional case that a clinical study center visit cannot be attended, a phone call by the investigator will be made to evaluate safety, in combination with scheduled clinical study center visits.

Each subject will have a screening period of maximum 28 days. The duration of study treatment for individual subjects will vary from 52 weeks for the last enrolled subject to e.g. 132 weeks for the first enrolled subject (assuming a recruitment period of 80 weeks, the actual duration will depend on the actual time to recruit subjects for the study). A follow-up visit (at the clinical study center or by phone call, decided by the investigator) is planned 4 weeks after the EoST/end of study assessment (EoSA) visit.

At the end of this study, treatment with IP in an optional extension study (under a separate study protocol) may be offered to all eligible subjects, provided Independent Ethics Committee (IEC)/Institutional Review Board (IRB) and Competent Authority approvals for such an extension are granted.

To protect the safety and integrity of the study data, an independent data monitoring committee (IDMC) will be implemented, as well as a clinical endpoint adjudication committee (CEAC). Charters are in place for all committees.

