### 6.2. Analysis Periods for Non-visit Data

These analysis periods are to be used for allocation of events into periods (e.g. adverse events).

Analysis period	Start period	End period
Screening	Date of signing the ICF.	1 day before the date of first dose of IP
Treatment	First dose of IP date.	Last dose of IP date + 30 days.
Follow-up	Last dose of IP date + 31 days.	Study termination date. Note: if the study termination date is before the last dose of IP + 30 days no follow-up period will be created.

Table 1Analyses Periods for Non-Visit Data

Note:

- If times are collected or other information with respect to timing (e.g. before or IP intake) this information will be taken into account in addition to the dates.
- The last analysis period in case of early termination will always end by the study termination date (date of last contact in the study or last known alive).

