### 7.2. Calculation of Percentages

For event-type data (e.g. adverse events), the denominator for calculation of percentages will be all subjects in the analysis set and analysis period. For other data (e.g. worst-case analysis of assessments, demographic data), the denominator will be all subjects with (postbaseline) data for the parameter, in the analysis set and analysis window/period. Missing values will not be included in the denominator count.

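### The TEAE differences from placebo rest on crude percentages in a window that closes 30 days after last dose, so unequal drug discontinuation by arm, if it occurs, can bias them, and most terms have no time-adjusted contrast

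*SAP*

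**What the plan says.** SAP Section 9.4.1.6.1 sets the between-arm comparison for treatment-emergent events: "The table will also include the difference in percentage of subjects with an TEAE from placebo for each of the two dose groups", with 95% intervals by the Miettinen-Nurminen method. The same contrast is repeated by system organ class and preferred term for events reaching 5% in any arm.

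Three other places fix what these percentages mean.
- **Window.** Section 9.4.1.1 takes as treatment-emergent "All adverse events starting on or after the first dose of IP and up to the last dose plus 30 days". Section 6.2 ends the treatment period at "Last dose of IP date + 30 days".
- **Denominator.** For event-type data, Section 7.2 says "the denominator for calculation of percentages will be all subjects in the analysis set and analysis period". It counts subjects, not person-time.
- **Exposure.** Section 9.2.6 reports "Patient-years of exposure to IP by treatment group and overall", but no AE table uses it.

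Section 9.4.1.6.1 also plans time-to-event displays: "Kaplan-Meier estimates will be presented graphically and in tabular format for the following time to first event endpoints, by treatment". They cover first TEAE, first serious TEAE and first TEAE leading to stopping IP. Section 9.4.1.6.2 repeats the crude tables and differences for all AEs to the end of the study. Outside the safety section, Sections 9.3.3 and 9.3.4 use events per 100 patient-years for hospitalization and other time-to-event endpoints. No such rate is planned for AEs.

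**The concern.** A crude percentage compares arms fairly only if the arms are observed for similar lengths of time. Here observation for TEAEs stops soon after the drug does. If one arm stops drug earlier for reasons unrelated to the event being counted, it has less time in which to record that event, and its percentage falls although the risk per unit time is the same.

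The documents do not say that discontinuation differs by arm. It is foreseeable, because Protocol Section 4.5.4 requires IP to be stopped for, among others, liver enzyme, QTcF and bile acid findings. These may not occur equally often on 600 mg, 200 mg and placebo.

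The stake is the reading of harm. SAP Section 1 says the studies were halted because the IDMC judged that benefit-risk no longer supported them, and it keeps safety among the endpoints still to be analyzed. Every AE contrast in the safety section that carries a confidence interval is a difference in crude percentages.

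**Working it through.** There is no plan figure to reproduce: neither document states an AE rate, a discontinuation rate or time at risk by arm. The check asks what the planned contrast would show under stated assumptions.

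**From the documents.** The window runs from first dose to last dose + 30 days. Treatment durations "vary from 52 weeks for the last enrolled subject to e.g. 132 weeks for the first enrolled subject" (SAP Section 2.3). For allocation, "A total of approximately 750 subjects will be randomized in a 1:1:1 ratio", about 250 per arm.

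**Assumed.** Constant event hazard λ, identical in both arms: 0.25 per year (serious TEAEs) or 0.05 per year (one preferred term). One-year IP discontinuation p of 15% on placebo and 15%, 25% or 35% on active, independent of the event. Planned end of treatment uniform between 52 and 132 weeks.

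**Formula.** Let μ = -ln(1-p), s = λ + μ, a = 52/52.18 = 0.9966 years, b = 132/52.18 = 2.5297 years, τ = 30/365.25 = 0.0821 years.
- E = (e^(-sa) - e^(-sb)) / (s(b-a))
- Crude percentage = 1 - e^(-λτ) × (μ + λE)/s

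**Serious TEAEs, λ = 0.25, e^(-λτ) = 0.9797.**
- p = 15%: μ = 0.1625, s = 0.4125, E = 0.4913; 1 - 0.9797 × (0.1625 + 0.1228)/0.4125 = 32.2%
- p = 25%: μ = 0.2877, s = 0.5377, E = 0.3986; 1 - 0.9797 × (0.2877 + 0.0997)/0.5377 = 29.4%
- p = 35%: μ = 0.4308, s = 0.6808, E = 0.3150; 1 - 0.9797 × (0.4308 + 0.0788)/0.6808 = 26.7%

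| Active p (placebo 15%) | Mean time at risk ignoring events, active (placebo 1.60 y) | Serious: active minus placebo | Preferred term: active minus placebo |
|---|---|---|---|
| 15% | 1.60 y | 0.0 | 0.0 |
| 25% | 1.45 y | -2.8 | -0.7 |
| 35% | 1.30 y | -5.6 | -1.4 |

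Differences are in percentage points, from unrounded values. A simulation of 2,000,000 subjects per arm agreed within 0.1 point.

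**Precision.** With 250 per arm, the Miettinen-Nurminen intervals for the serious-TEAE differences are -10.9 to 5.3 (25%) and -13.5 to 2.4 (35%).

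**Harm that could be hidden.** A true hazard ratio of about 1.11-1.12 (25%) or 1.24-1.27 (35%) would show a crude difference of zero.

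**Person-time rate.** Events divided by time from first dose to first event, or to last dose + 30 days, give about 25.0 against 25.0 and 5.0 against 5.0 per 100 patient-years in every scenario.

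**Reversed direction.** Suppose the extra stops on active are themselves TEAEs, at an added hazard of 0.06, 0.12 or 0.27 per year. The earlier-stopping arm then shows 5.6, 10.6 or 21.1 points more.

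**Kaplan-Meier censoring.** Section 9.4.1.6.1 gives no censoring rule. Sections 9.3.3 and 9.3.4 censor at last contact. Applied to events that count only to last dose + 30 days, that rule keeps subjects in the risk set when they can no longer have a counted event. For serious TEAEs at 52 weeks, the simulated difference is then -1.0 point (25%) or -2.0 points (35%), again with equal hazards.

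**The case against.** The strongest reply is that the SAP already offers several ways around the problem.

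- **End-of-study tables.** Section 9.4.1.6.2 drops the 30-day cut and repeats the differences and intervals, also by preferred term. With equal hazards it shows a difference of about zero. This stands, but only if subjects who stop drug stay in follow-up. SAP Section 2.3 encourages that, and excepts those lost or withdrawing consent. The tables also mix off-drug time into the comparison.
- **Kaplan-Meier.** Besides the three summary events, Section 9.4.1.6.4 plans curves for nintedanib- and pirfenidone-type events, and Section 9.4.2.9 for liver enzyme thresholds. This stands for those terms. No between-arm interval is specified for the curves, and other terms have none.
- **Cox models.** Section 9.3.3.1 analyzes mortality, hospitalization and acute exacerbation in the manner of Section 9.3.3, with hazard ratios and intervals. Most of what a fatal-TEAE rate would show is covered there. A reader might infer that crude differences are the only comparison bearing on harm; that is not so.
- **Exposure reporting.** Patient-years (Section 9.2.6) and Kaplan-Meier time on treatment (Section 9.2.2) appear by arm, so a reader could form rough rates, but without intervals and not by term on the right time at risk.

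Two further replies stand in full. The shifts are smaller than the roughly 8-point half-width of the intervals, and Section 9.4 plans no formal safety testing. A rate per 100 patient-years assumes a roughly constant hazard: if events cluster early, it makes the arm with shorter exposure look worse. That is a reason not to let rates replace the crude results.

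**Conclusion.** The gap is real but limited. The TEAE contrasts are crude, their window depends on when drug stops, and general system organ class and preferred terms have no time-adjusted comparison. Under equal true hazards of 25 per 100 patient-years and assumed one-year discontinuation of 15% against 25-35%, the serious-TEAE difference is off by about 3 to 6 points in favour of active; for a term at 5 per 100 patient-years it is off by about 1 point. All hazards and discontinuation rates are assumptions.

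Three stronger readings are not supported.
- That time at risk does differ by arm: neither document gives exposure or discontinuation by arm.
- That the 52-to-132-week spread, or the halt, itself creates the bias: these follow enrolment date and calendar time, which randomization balances, and with equal discontinuation the bias is zero.
- That the earlier-stopping arm must look safer: when the extra stops are themselves TEAEs, totals that include them move the other way.

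This is a worthwhile supplement to the safety tables, not a flaw that invalidates them.

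**What to change.** Keep the crude differences. Beside them, in Section 9.4.1.6.1, add incidence per 100 patient-years at risk, counting time from first dose to the earlier of first event and last dose + 30 days. Give rate differences and 95% intervals against placebo for serious TEAEs, fatal TEAEs, and system organ classes and preferred terms at 5% or more. State that the TEAE Kaplan-Meier curves are censored at the earlier of last dose + 30 days and last contact.

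Say in the text that the rates assume a roughly constant hazard and are read together with the crude and Kaplan-Meier results, not as the main contrast.

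The cost is a few table columns. Event onset days (Section 9.4.1.5) and period dates (Section 6.2) are already derived. The denominators would also show time at risk by arm, which helps because Section 9.1 drops the summary of analysis-period durations.
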